7.1.3 Randomization of Study Treatments

The treatment arm (test or reference) for each patient during the study will be assigned according to randomization list. This randomization list will be prepared reviewed and finalized in a blinded manner and will not be accessible to the study team involved in the study conduct. The treatment will be assigned at the time of randomization, after confirming patient's

eligibility. Patients will be randomized in a 1:1 ratio to either LUBT010 or Lucentis®. Patients who qualify for study randomization will have a unique randomization number. Randomization will be stratified by iris color (light colored, not light colored) to maintain treatment balance within strata. Randomization block size will be specified in the randomization plan and will not be shared with investigators. After completion of required number (600 patients), some patients who qualify in screening may not be enrolled in the study.

7.1.4 Blinding of Study Treatment

This study will be performed in a double-blind manner. In order to maintain the double-blind status of the study, packaging of LUBT010 will have similar appearance to the Lucentis®. Investigator/ other members of staff involved in the study and patients will remain blinded to the treatment arm during the study.

7.1.4.1 Breaking the Blind for Safety Reason

Randomization codes, indicating the treatment randomization for each randomized patient, will be available to the Investigator(s)/site, if required, as mentioned below.

The randomization code should not be broken except in medical emergencies when the appropriate management of the patient requires knowledge of the treatment arm to meet regulatory requirements (e.g., in the case of SAE or death). In this case individual randomization codes, indicating the treatment arm for each randomized patient, can be made available to the Investigator(s).

If possible, there should be a discussion among the Investigator and Lupin study team and/ or the medical expert prior to breaking the code. If the blind is broken, the date, time, and reason for unblinding must be recorded. If the treatment information is unblinded, the Investigator should document and report the action to Lupin. Patients will immediately be discontinued from the study by the Investigator and the EOS visit assessments will be performed.

7.1.4.2 Breaking the Blind for Regulatory Authorities

If requested by regulatory agency, the blind can be broken and the unblinded safety information will be provided to the regulatory authority. In such cases, the patients can continue participation in the study.

7.1.5 Patient Compliance

For this study-purpose the per protocol compliance to study medication will be defined as all those randomized patients who receive all the 12 intravitreal injections of 0.05 mL of 10 mg/mL ranibizumab in the study eye.

7.1.6 Concomitant Therapy

Prohibited Medications: Other therapies for the treatment of AMD, including but not limited to Verteporfin photodynamic therapy, Pegaptanib, Bevacizumab, Aflibercept or Brolucizumab will not be allowed in the study eye during the study. Anti-VEGF therapy, other than ranibizumab (approved innovator product) for treatment of exudative AMD in the respective country, will not be allowed in the non-study eye during the study. Other biologics will not be allowed during the study. Any other experimental therapy for treatment of AMD will not be allowed in study eye or non-study eye during the study.

Allowable Medications: Any other medications/ treatments required by the patient and not expected to interfere with study assessments will be allowed on a case-by-case basis and as deemed appropriate by the Investigator. Therapies like thermal laser and verteporfin PDT for AMD can be allowed in the non-study eye at the discretion of the Investigator. Anti-VEGF therapy [ranibizumab (approved innovator product) for treatment of exudative AMD in the respective country] can be administered in non-study eye as needed when deemed to be clinically justified in the opinion of the Investigator. Supplementation with antioxidant & minerals (non-investigational treatments) (e.g. lutein zeaxanthine or beta carotene, Vitamin C, E, and Zinc) can be allowed¹⁷.

7.2 IP MANAGEMENT

7.2.1 IP Dosage Form and Strength

LUBT010/Lucentis® for Intravitreal injection is supplied as single-use vial designed to deliver 0.05 mL of 10 mg/mL ranibizumab. The details of the study medications are given in Table 3.

Table 3: IP Details

Study Medication	Dosage Form and Strength	Sourced from
LUBT010	Supplied as single-use, 2-cc glass vial containing 2.3 mg of ranibizumab in 0.23 mL solution designed to deliver 0.05 mL of 10 mg/mL ranibizumab, by intravitreal injection.	Lupin Limited (Biotech Division), [name]
EU-approved Lucentis®	Supplied as single-use, 2-cc glass vial containing 2.3 mg of ranibizumab in 0.23 mL solution designed to deliver 0.05 mL of 10 mg/mL ranibizumab, by intravitreal injection.	(Marketing Authorization Holder in UK) Novartis Europharm Limited [name].

7.2.2 IP Packaging and Labelling

A single-use, 2-cc glass vial (LUBT010 or Lucentis®) will be packaged individually in cartons along with syringes and needles. The packs will be labeled as per regulatory requirements. Each pack will have unique identification number.

Each patient will be assigned a randomization number and IP pack containing either LUBT010 or Lucentis® will be dispensed.

Labels will be prepared in accordance with Good Manufacturing Practice and local regulatory guidelines. The label text will be translated into local language. The labels shall contain appropriate information as per the local regulatory requirements including but not limited to product content and strength, batch No, manufacture date, retest/ expiry date, storage information, route of administration, statements like “For Clinical Trial Purpose Only”.

7.2.3 Storage

Investigational product (Ranibizumab) injection should be stored under refrigeration at 2°-8°C (36°-46°F) at all times. The product should be kept in the original carton to protect from light

until the time of use. Do Not Freeze. Prior to use, the unopened vial may be kept at room temperature (25°C) for up to 24 hrs. Do not use beyond the expiry date which is stated on the carton/vial. Do not use any pack if it is damaged. IP vials should be used once only, and any unused portion left in the vials should not be considered for use.

7.3 IP Supply, Handling and Accountability

The Sponsor/ designee will arrange for the supply, handling, and management of IPs. The Sponsor/ designee will supply sufficient quantity of IPs, for administration to randomized patients at each site. Blinded IP will be shipped under appropriate storage conditions to the Investigator sites.

The designated study personnel must take the responsibility to keep a record of the IP management.

Sites will receive IP with appropriate documents and store according to the storage requirements. Adequate records of IP for receipt, accountability, usage and disposal, or return to Sponsor will be maintained at respective Investigator site. Investigational product will be administered to eligible patients according to randomization schedule.

Pharmacist/ designated study personnel will dispense the IP for administration. The unused IP will be kept in their original containers. The sites will return any unused IP to the Sponsor or destroy on site (as mutually agreed between Sponsor and sites), once the site's monitor has reviewed and confirmed drug accountability, or at the end of the study.

Used IP vials should also be kept in the original packing and this should also be returned/ destroyed on site (as mutually agreed) to Sponsor after confirmed drug accountability by site monitor.

The IPs should not be used for purposes other than those conforming to this protocol.

8 ASSESSMENT OF EFFICACY

8.1 Efficacy Endpoints

Primary Efficacy Endpoint:

Mean change in BCVA from baseline in the study eye at the end of 12 months, assessed with the ETDRS chart.

Secondary Efficacy Endpoints:

- Mean change in BCVA from baseline in the study eye at the end of 3 months, assessed with the ETDRS chart.
- Mean change in BCVA from baseline in the study eye at the end of 6 and 9 months, assessed with the ETDRS chart.

Exploratory Endpoint:

- Mean change from baseline in NEI-VFQ-25 Version 2000 (interviewer administered) scores at of 3, 6, and 12 months.

8.2 Efficacy Variables

Mean change in BCVA from baseline in the study eye by ETDRS chart will be measured as primary and secondary endpoints. BCVA is measured by the number of letters a patient could correctly read on an eye chart; hence an increased score indicates improvement in acuity.

For this study the ETDRS chart (including original Sloan letter chart or number chart) will be used for visual acuity measurement. Standard procedures will be followed for ETDRS testing across sites. The details of the testing procedures will be described in a separate procedures' manual. It is must that testing is done prior to dilating eyes with refraction error corrected with lenses. The ETDRS testing will be standardized and made uniform across sites.

The NEI-VFQ-25 Version 2000 will be administered by the interviewer at baseline (Day 1), 3, 6, and 12 months, which is a measure of subjective response and compliments the objective findings of BCVA.

9 ASSESSMENT OF SAFETY

Following safety parameters will be assessed,

- AE assessment, ocular and non-ocular (as per National Cancer Institute Common Terminology Criteria for Adverse Events [NCI CTCAE V5])
- Ophthalmic examination
- Physical and systemic examination
- Vital signs
- ECGs
- Laboratory parameters: Blood (hematology and biochemistry) and urinalysis

9.1 Adverse Events

9.1.1 Definitions

The definitions for AEs and SAEs are given below. It is of the utmost importance that staff involved in the study is familiar with the content of this section. The Principal Investigator is responsible for ensuring this.

9.1.1.1 Adverse Event

An AE is defined as any untoward medical occurrence in a patient or clinical investigation patient administered a pharmaceutical product and which does not necessarily have a causal relationship with this treatment. An AE can therefore, be any unfavorable and unintended sign, symptom, or disease (including intercurrent illness), deterioration of a pre-existing illness, accident, any suspected drug reaction, or a clinically relevant change of laboratory values temporally associated with the use of a medicinal (investigational) product, whether or not related to the medicinal (investigational) product and/or study treatment.

A treatment-emergent AE (TEAE) will be defined as an AE that begins or worsens in severity after at least one dose of study drug has been administered.

See Section 9.7 below for the instances where a pregnancy should be reported as an AE.

9.1.1.2 Serious Adverse Event

An SAE is defined as, any untoward medical occurrence that at any dose:

- Results in death.
- Is life-threatening.

An AE or adverse reaction is considered “life-threatening” if, in view of either the Investigator or Sponsor, its occurrence places the patient at immediate risk of death. It does not include an event that, had it occurred in a more severe form, might have caused death.

- Requires in-patient hospitalization or prolongation of hospitalization
- Results in persistent or significant disability/incapacity.
- Is a congenital anomaly/birth defect.
- Consists of any other medically important condition.

Medical and scientific judgment should be exercised in deciding whether expedited reporting is appropriate in other situations, such as important medical events that may not be immediately life-threatening or result in death or hospitalization but may jeopardize the patient or may require intervention to prevent one of the other outcomes listed in the definition above. These should also usually be considered serious. Examples of such events are intensive treatment in an emergency room or at home for allergic bronchospasm; blood dyscrasias or convulsions that do not result in hospitalization; or development of drug dependency or drug abuse.'

9.1.2 Recording and Collection of Adverse Events

It is the responsibility of the Investigator to collect all AEs (both serious and non-serious) derived from spontaneous, unsolicited reports of patients, by observation, and by routine open questions.

AE reporting will extend from date of informed consent until completion of the final visit (EOS). Any ongoing AE at EOS visit (Day 360 ± 2 days) should be followed until the outcome is evident and resolved, clinically stabilized or a plausible explanation has been found.

Pre-existing diseases including deranged laboratory values (before participating in the study) are not considered to be AEs, unless the disease worsens during the study period. Concomitant diseases detected during screening or prior to randomization will be recorded in the medical history eCRF.

Signs and symptoms clearly associated with the disease under study (including symptoms of disease progression) should be reported as AEs if they are newly emergent (i.e., findings not previously observed in the patients), or are determined by the Investigator as severe or a worsening, or if the Investigator considers deterioration of disease-related signs and symptoms to be caused directly by the study drug.

Abnormal laboratory values/ ECGs/ vital signs/ ophthalmic/ physical &systemic examination should be reported as AEs only if the Investigator considers the abnormality as clinically relevant or significant or believes that the abnormality should be reported as an AE.

Any dose (and associated symptoms) given to the patient that exceeds the dose prescribed to the patient has, at a minimum, to be recorded as a non-serious AE in the patient file and eCRF. Any case of overdose leading to an AE or SAE should be reported to Medical Monitor according to reporting requirements. In case of an accidental overdose, the patient should be monitored by the Investigator for any adverse clinical events including IOP, as deemed necessary by the Investigator.

After completion of all scheduled visit assessments, the Investigator must document any AEs arising from these assessments. In case of an SAE, the Investigator must also complete an SAE report form and report it to safety contact, as described in Section 9.1.3.3.

All AEs will be recorded in eCRF regardless of the causal relationship to the study drug.

All AE records should contain AE term/ AE diagnosis, date of onset, severity, relationship to the study drug, outcome, date of recovery or outcome, action taken with respect to study drug, action taken with AE, AE leading to discontinuation of patient from study, and whether the event is classified as serious.

The categorization of action taken with IP, outcome and action taken for AE is described below:

Categories of Actions Taken with IP	Categories of Outcome*	Categories of action taken for AE

 • Dose Delayed • Drug withdrawn temporarily • Drug withdrawn permanently • Unknown • Not applicable 	
 • Recovered/Resolved • Recovered/Resolved with sequelae • Recovering/Resolving • Not Recovered • Fatal • Unknown 	
 • None • Medication • Hospitalization • Non-drug treatment • Patient withdrawn • Other

*If there is more than one AE, only the AE leading to death will be attributed with a fatal outcome.

In cases where multiple symptoms and signs can be described as one diagnosis (disease), the name of the diagnosis is reported as the name of the AE.

For example, running nose, cough, and sore throat: The 3 symptoms can be described as a series of symptoms of "common cold"

⇒ Common Cold or Upper Respiratory Tract Infection

The Investigator must continue to follow-up the patient with all AEs regardless of the causal relationship to the study drug until the AE has resolved or until the condition stabilizes to an acceptable level or is determined to pose no issue, or until follow-up is no longer feasible.

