6.3.1.2.6 Day 360 \pm 2 days (EOS/Early Discontinuation)

The following procedures will be performed at Day 360 \pm 2 days or at the time of withdrawal/discontinuation prior to 12 months of treatment:

- Vital signs assessment
- Perform physical and systemic examination
- Perform clinical laboratory assessment (hematology, biochemistry, and urinalysis)
- Perform Urine pregnancy test in females of childbearing potential only
- Record ECG
- AE assessment
- Record changes in concomitant medication/treatment
- Ophthalmic Examinations: Unless otherwise stated these will be done for both the eyes
 - Refraction assessment
 - BCVA using ETDRS*
 - Ophthalmoscopic examination
 - Slit lamp examination
 - IOP measurement
- Immunogenicity (anti-drug antibody) assessment
- Interviewer administered NEI-VFQ-25

Note: * notes of screening visit to be followed.

Post EOS visit or discontinued patients (anytime during study) may be shifted to appropriate standard therapy by the Investigator depending on the disease condition.

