6.4.3 Withdrawal and Discontinuation of Patients

Patients may discontinue the study at any time without any penalty or loss of benefits to which the patient is otherwise entitled. For all patients withdrawn from the study, efforts will be made to ascertain the reason for withdrawal.

A withdrawn patient is one who meets any of the following withdrawal criteria stated below and whose study participation is discontinued. The reasons for patient withdrawal will be recorded in the electronic case report form (eCRF).

In case of early discontinuations/ premature termination of the study all EOS investigations should be done on the day of termination as far as possible.

Criteria for Withdrawal from Study:

- The patient is not willing to continue participation in the study (withdraws consent).
- Lost to follow-up

General Criteria for Treatment Discontinuation

- The patient needs emergency treatment or is unable to continue participation in the trial due to the exacerbation of their symptoms.
- Inability of patient to comply with the Protocol for any reason.
- The patient becomes pregnant during the study period.
- In the opinion of the Investigator or sub-investigator, the patient should be discontinued due to AEs (including progressing complications) or safety reasons.
- Other reasons due to which the patient should be discontinued, in the opinion of the Investigator or sub-investigator.

Ocular Criteria:

Treatment Discontinuation:

Treatment should be discontinued in patients with rhegmatogenous retinal detachment or stage 1 to 4 macular holes.

Dose Withholding Criteria:

The dose should be withheld/postponed, and treatment should not be resumed earlier than the next scheduled treatment in the event of:

- a decrease in best-corrected visual acuity (BCVA) of ≥ 30 letters in study eye compared with the last assessment of visual acuity;
- an IOP of ≥ 30 mmHg before dosing;
- a retinal break;
- a subretinal hemorrhage involving the center of the fovea, or, if the size of the hemorrhage is $\geq 50\%$, of the total lesion area;
- performed or planned intraocular surgery within the previous or next 28 days

Based on OCT result, should the investigator decide to withhold an injection for potential safety concern, a pro-re-nata (PRN) or treat-and-extend regimen can be used.

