6.4.5 Other Patient Restrictions

Patients may not participate in another clinical study that involves an investigational product (IP) during this study.

Females patient currently pregnant or breast feeding or planning to conceive are not allowed to be included in the study. Female patients should refrain from becoming pregnant during the study period and should use effective contraception during the study and 3 months after the last dose of study drug.

For concomitant medications/treatments which are restricted during the study, please see Section 7.1.6.

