9.1.3.3 Reporting of Serious Adverse Events

All SAEs occurring after the time of informed consent until the final visit (Day 360 visit) must be reported.

All SAEs should be reported by the Investigator to the Safety Contact via Email (at [contact]) or telephone within 24 hours, regardless of the causal relationship with the IPs (following knowledge of the SAE). After receiving reports of the SAEs, the Safety Contact should communicate with the Investigator to get additional information for evaluation of SAEs.

The Investigator is responsible for reporting SAE (initial report, analyzed report as well as follow-up information) to the Ethics Committee (EC) and/or applicable regulatory authority as per applicable local regulatory requirements of participant countries. All SAEs shall be reported by Investigator/ Sponsor/ Sponsor designee as per applicable regulatory requirements.

The Details of Safety Contact:

[REDACTED]

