9.7 Pregnancy

Pregnancy alone is not regarded as an AE unless there is a suspicion that the study drug may have interfered with the effectiveness of a contraceptive medication.

Elective abortions without complications should not be handled as AEs, unless they were therapeutic abortions. Hospitalization for normal delivery of a healthy newborn should not be considered an SAE.

If a pregnancy or a positive pregnancy test is reported for a patient during study participation, the study drug must be immediately discontinued.

Pregnancies occurring during the study until EOS must be reported. All pregnancies must be reported to the Sponsor within 24 hours after becoming aware of the pregnancy, using the initial pregnancy report form. The Investigator should counsel the patient; discuss the risks of continuing with the pregnancy and possible effects on the fetus. The Investigator must follow-up and document the course and outcome of all pregnancies, even if the patient was discontinued from the study or if the study has finished.

All outcomes of pregnancy must be reported by the Investigator to the Sponsor on the pregnancy outcome report form within 30 days after he/she becomes aware of the outcome.

Any SAE that occurs during a pregnancy must be recorded on the SAE report form (e.g. maternal serious complications, spontaneous or therapeutic abortion, ectopic pregnancy, stillbirth, neonatal death, congenital anomaly, or birth defects) and reported in accordance with the procedure for reporting of SAEs.

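### No minimum safety-reporting interval after the last injection is set for early discontinuers, their SAE end date is ambiguous, and pregnancy reporting ends before the contraception period does

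*Combined protocol and SAP*

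**What the plan says.** - **New AEs.** Section 9.1.2: "AE reporting will extend from date of informed consent until completion of the final visit (EOS"). The next sentence of that section labels EOS as Day 360 ± 2 days.
- **SAEs.** Section 9.1.3.3: "All SAEs occurring after the time of informed consent until the final visit (Day 360 visit) must be reported".
- **EOS after early stopping.** Section 6.4.3 says that "all EOS investigations should be done on the day of termination as far as possible", and a footnote to Table 1 says the same. Section 6.3.1.2.6 schedules the EOS procedures on Day 360 or "at the time of withdrawal/discontinuation prior to 12 months of treatment". After emergency unblinding, Section 7.1.4.1 says: "Patients will immediately be discontinued from the study by the Investigator and the EOS visit assessments will be performed".
- **Grounds for stopping.** Among them, Section 6.4.3 lists the opinion of the investigator that "the patient should be discontinued due to AEs (including progressing complications) or safety reasons".
- **Contact between visits.** One safety visit is fixed, between Day 2 and Day 9 after the first injection. After later injections a visit or call is at the investigator's discretion (Section 6.3.1.2.4).
- **Events already present.** Sections 9.1.2 and 9.1.3.4 require AEs and SAEs that are ongoing at EOS to be followed until they resolve, stabilise or are explained.
- **Pregnancy.** Section 9.7: "Pregnancies occurring during the study until EOS must be reported". Section 6.4.5 says that female patients "should use effective contraception during the study and 3 months after the last dose of study drug". Pregnancies already known are followed even after the study ends.

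**The concern.** Comparative safety is a secondary objective (Section 4.2). The end of AE collection is tied to a visit and not to the last injection. For completers the two are about a month apart. For early discontinuers the visit moves to the day of stopping, so the time observed after the last injection depends on when the patient stops.

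Adverse events are among the grounds for stopping, so part of the shortfall can fall on patients who were stopped for safety. The protocol itself asks for watchfulness for endophthalmitis after each injection (Section 7.1.2) and names a theoretical risk of arterial thromboembolic events (Section 9.1.5.1). A new event of either kind that begins after an early EOS is outside the AE rule as written.

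The TEAE definitions (Sections 9.1.1.1 and 11.8.1.1) have no end date. AEs are to be summarised as counts and percentages of patients, and the protocol describes no adjustment for unequal observation time. Differences in window length would therefore pass straight into those tables.

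**Working it through.** **Planning figure.** Section 11.1 takes 600 randomized patients and 7% dropout. 600 × 0.07 = 42, and 600 − 42 = 558, the plan's evaluable number. So 42 is the planned count of dropouts of every kind and at every time.

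**Days from last injection to end of AE collection, if EOS is the end:**

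| Patient | Calculation | Days |
|---|---|---|
| Completer, nominal | 360 − 331 | 29 |
| Completer, shortest within windows | 358 − 333 | 25 |
| Completer, longest within windows | 362 − 329 | 33 |
| Stops at the next scheduled visit, before dosing | e.g. 31 − 1 | 30 |
| Stops 14 days after an injection | 14 (29 − 14 = 15 short) | 14 |
| Stops 7 days after an injection | 7 (29 − 7 = 22 short) | 7 |
| Stops on an injection day, after dosing | 0 (29 short) | 0, apart from same-day checks |

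The shortfall therefore runs from none to 29 days, according to when the patient stops. The documents give neither the timing of stopping nor the reasons, so the table cannot be turned into an expected number of patients.

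**Why the first weeks matter.** Section 3.2 gives a vitreous half-life of about 9 days. Assuming simple first-order elimination, the fraction remaining is 0.5^(days/9): 58% at 7 days, 34% at 14 days and 11% at 29 days. This shows that a patient who stops early is still exposed. It says nothing about event rates.

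**SAE end date, side by side.** Section 9.1.2 ends AE collection at EOS. Section 9.1.3.3 ends SAE reporting at a final visit identified as Day 360. Sections 6.3.1.2.6 and 6.4.3 move the EOS assessments to the day of stopping. For an early discontinuer, SAE reporting can be read as ending at the early EOS or as staying open to Day 360. Section 6.4.3 separates stopping treatment from leaving the study, but does not say that patients who stop treatment remain in follow-up. It does not settle the question.

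**Pregnancy.** Taking 3 months as about 90 days, a completer has 90 − 29 = 61 days in which contraception is required but a new pregnancy need not be reported. For a patient who stops on an injection day it is up to 90 − 0 = 90 days. Entry requires age 50 or over (Section 6.4.1), so few patients are of childbearing potential. The documents do not give their number.

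Sample size and power are not affected.

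**The case against.** Much of the case on the other side stands.

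- A patient stopped because of an AE has that AE on record, and it must be followed. Only a new event that begins after an early EOS is at risk.
- Scheduled visits include AE, visual acuity and pressure checks before dosing. A patient stopped at that point has about as much observation as a completer.
- On a literal reading of Section 9.1.3.3, SAE reporting may stay open to Day 360.
- Patients are told to report symptoms of endophthalmitis promptly (Section 7.1.2), and a call after any injection is permitted.
- Section 9.1.3.5 leaves details of reporting SAEs and significant AEs to a Safety Monitoring Plan that is not among these documents. It may set a later contact.
- Some of the 42 planned dropouts will have withdrawn consent or been lost to follow-up, and no call will reach them.

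A reader might go further and infer that post-injection events are lost in early discontinuers generally, and above all in those with safety problems. The first three points rule that out as a general statement. A reader might also infer a biased comparison between arms. That would need stopping to differ by arm, and nothing in this double-blind plan indicates that it will. Nor can a total of lost patient-days be given, since it would need a distribution of stopping times that the documents do not contain.

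What the objection does not remove is the absence of any required minimum. Discretionary calls and follow-up of known events do not extend the collection of new ones, and a literal Day 360 reading for SAEs would leave non-serious AEs on a different rule.

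**Conclusion.** The point holds in a limited form, as a change worth making at low cost. For early discontinuers the protocol sets no minimum safety-reporting interval after the last injection, against 29 days (25 to 33) for completers. New events can go unrecorded in those who stop soon after an injection. The SAE end date for these patients is ambiguous between Sections 9.1.2 and 9.1.3.3. Reporting of new pregnancies is shorter than the contraception period for every patient of childbearing potential, completers included.

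At most about 42 of 600 patients are concerned by the AE and SAE part if dropout is as planned. The number who stop within days of an injection is unknown and will be smaller. The conclusion assumes that the early-discontinuation visit counts as EOS for AE reporting, as the heading of Section 6.3.1.2.6 suggests, and that the Safety Monitoring Plan does not already set a fixed contact.

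**What to change.** 1. In Sections 9.1.2 and 9.1.3.3, state one end of AE and SAE collection for every treated patient: EOS or 29 days after the last injection, whichever is later. The 29 days are the protocol's own interval from Day 331 to Day 360. For a completer at the short end of the windows this keeps reporting open at most 29 − 25 = 4 days past EOS.
2. Keep the early-discontinuation visit as it is. Add one telephone contact of the type in Section 6.3.1.2.4 at the end of that period for early discontinuers, where consent allows.
3. Record the start date of any later standard therapy, and flag or separate events that begin after it in the TEAE summaries. The present TEAE definitions would otherwise attribute them to the randomized arm.
4. In Section 9.7, align the reporting period with the 3-month contraception period in Section 6.4.5 by asking patients to report pregnancies to the site.

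The cost is amendment wording, at most about 42 calls at the planned dropout rate, one extra date in the eCRF and a small addition to the TEAE tables. Some calls will fail or be declined, some recorded events will follow a switch of therapy, and some pregnancy reports may arrive after EOS, possibly after the last patient's last visit. Section 9.7 already provides for following known pregnancies beyond study end, so a route for late reports exists.
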